8.12 Adverse Events

While the overall IVF procedure may involve several visits and procedures, the first time the subject or user has any encounter with the MIRI-TL and CultureCoin is when the embryos are first loaded onto the MIRI-TL for imaging. Adverse

events for the subject or user will be reported from the point of embryos being placed in the MIRI-TL through study completion for each subject. An adverse event will be followed until resolved or stabilized at a level acceptable to the investigator.

Events well documented to be associated with ART/IVF procedures (as outlined in each clinic's consent for IVF procedures) will not be collected as adverse events under this protocol. Other common non-study or non-device related, minor health complaints will not be collected as adverse events (for example: colds, sprains, headaches).

The investigator should follow the reporting requirements of the reviewing IRB/REB for all adverse events (including serious and unanticipated adverse device effects). Documentation of any IRB and Esco Global notifications should be maintained in the site's clinical study files. It is recommended that acknowledgement of receipt from the IRB be maintained in the study file as well.

Adverse events will be reported to Esco Global and data collected will include the following:

- Date of adverse event
- Type of event and description
- Action/treatment taken
- Severity of event
- Seriousness of event
- Investigator's assessment as to the relationship of the AE to the MIRI-TL
- Investigator's assessment as to the relationship of the AE to IVF/ART procedures

Investigator's assessment if the event is a potential Unanticipated Adverse Device Effect (UADE)

Source documentation for adverse events must be collected and filed with the subject's medical chart. Refer to Section 10 – Adverse Event Definitions and Reporting for additional information. Because study procedures are limited to the noninvasive collection of clinical data, no Data Safety Monitoring Board will be established for this study.

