Indications for Use/Intended Use	The MIRI-TL is a purpose built embryo culture incubator using a built-in microscope and camera designed specifically for the continuous assessment of embryo development in-vitro . As images are digitally obtained and stored, a video can be generated to enable more objective and reliable grading criteria. This technology, in conjunction with the MIRI-TL Viewer allows for non-invasive viability evaluation and assessment allowing for better prediction of embryo developmental potential and implantation success. The MIRI-TL is CE marked for clinical use. The CultureCoin is intended to be used to hold human oocytes and embryos during handling and culture.
Study Purpose	The purpose of this study is to demonstrate and validate the non-inferior or superior safety and efficacy of the MIRI-TL compared to standard big-box incubators used for embryo culture.
Study Design	Prospective, observational, randomized, double-arm

Safety Measures	Adverse events and device malfunctions will be reported and summarized from the start of embryo culture through study exit.
------------------------	---

Number of Subjects	Up to 500 patients
Subject Population	Patients undergoing in vitro fertilization treatment who fulfill all eligibility criteria.
Eligibility Criteria	
Inclusion Criteria:
 
 • At least 18 years of age • Women undergoing in vitro fertilization treatment using their own or frozen oocytes • Fresh or Frozen Embryo Transfer • Fertilization by ICSI • At least 4 diploid (2PN) embryos at fertilization check • Willing to have all inseminated oocytes imaged by Miri • Willing to comply with study protocol and procedures • Willing to provide written informed consent 
Exclusion Criteria:
 
 • Fertilization using surgically removed sperm • History of cancer
Number of Sites	1
Study Duration	Expected study duration is 18 months including enrollment and follow-up. Subjects will be followed until pregnancy outcome has been determined (i.e. date of negative hCG test, 8-12 week clinical pregnancy ultrasound, or date of live birth, if pregnant).
Summary of Data Collection	
 • Enrollment: Demographics, IVF and pregnancy history • IVF Lab: Embryo morphology • Time-Lapse Imaging Data • Pregnancy test and Live Birth Outcome • Preimplantation Genetic Screening (PGS) Data, if applicable • Frozen Embryo Transfer (FET) Data, if applicable

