3.1 Primary Objective

- To collect safety and imaging data on the MIRI-TL and CultureCoin.

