8.11 Device Incidents

Any feedback in regards to the Miri- TL should be reported to Esco Global as soon as possible. Feedback may consist of any alleged deficiency related to the physical characteristics, identity, quality, durability, reliability, safety, effectiveness, or performance of the MIRI-TL and/or CultureCoin. Engineering and Quality will investigate device deficiencies and perform an evaluation to determine and document the root cause of any device deficiency. Reports will be filed in the MIRI-TL Study project file and/or in document control. The following data will be collected:

- Date and time incident first observed
- Associated Device(s)
- Description of incident
- Troubleshooting
- Outcome

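### Section 8.12 screens out consent-listed IVF events before causality is judged and gives the control arm no start point, so AE counts and device malfunctions alone cannot support the comparative safety claim

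*Combined protocol and SAP*

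**What the plan says.** The synopsis gives the study purpose as to "demonstrate and validate the non-inferior or superior safety and efficacy of the MIRI-TL compared to standard big-box incubators". Section 3.1 has one primary objective: "To collect safety and imaging data on the MIRI-TL and CultureCoin". The synopsis entry on safety measures names two things: "Adverse events and device malfunctions will be reported and summarized from the start of embryo culture through study exit".

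Section 8.12 sets the AE rules:

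- **Exclusion.** "Events well documented to be associated with ART/IVF procedures (as outlined in each clinic's consent for IVF procedures) will not be collected as adverse events". Minor complaints unrelated to the study or device are also left out.
- **Window.** Adverse "events for the subject or user will be reported from the point of embryos being placed in the MIRI-TL", and then until each subject completes the study.
- **Data items.** For AEs that are collected, the form asks for seriousness, relationship to the MIRI-TL, possible unanticipated device effect, and "Investigator's assessment as to the relationship of the AE to IVF/ART procedures".

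Section 8.11 runs a separate stream for device incidents involving the MIRI-TL or CultureCoin: "Feedback may consist of any alleged deficiency related to the physical characteristics, identity, quality, durability, reliability, safety, effectiveness, or performance".

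Pregnancy outcomes are collected elsewhere: hCG (8.6), intrauterine sacs and heartbeats at about 5-8 weeks (8.7), and ongoing pregnancy at about 8-12 weeks (8.8). Live birth is among the secondary objectives in 3.2.

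**The concern.** The device holds oocytes and embryos and has no contact with the woman. Harm to a patient would therefore act mainly through the embryo, as failed development, pregnancy loss, or an abnormal pregnancy or birth outcome. These also happen in ordinary IVF. In a randomised comparison, a device effect on them would appear as a higher frequency of a familiar event in one arm. An exclusion keyed to familiarity with IVF can discard that signal before the investigator is asked about causality.

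What is at stake is how a low AE count would be read. If excluded events include those the device could influence, few or no AEs says little about comparative safety, yet AEs are half of the stated safety measures. The other half, device malfunctions, exists only for the MIRI-TL.

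**Working it through.** The plan states no expected AE rate, safety margin, safety sample size or safety power, so there is no safety figure to reproduce. The check is mainly a comparison of sections, followed by an illustration on assumed rates.

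**1. Reach of the exclusion.** Section 8.12 ties it to the clinic's IVF consent and does not list the events. That form is not in the documents reviewed. Its absence here is not the defect; the defect is that the protocol delegates the boundary of its AE dataset to an outside list and adds no exemption. The seriousness, device-relationship and unanticipated-effect items cannot recover an excluded event, because they are completed only for AEs that are collected. Section 8.12 also points to a Section 10 for AE definitions, but Section 10 is the reference list, so no further definition narrows the rule.

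**2. Start of the window.** Under 8.1, control embryos go into a standard dish and incubator. Read literally, the start point in 8.12 never occurs for them. The synopsis start point, the beginning of embryo culture, applies to both arms. The two passages must be reconciled.

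**3. What the safety measures compare.** Device incidents (8.11) concern the MIRI-TL and CultureCoin, with no control-arm counterpart. Pregnancy outcomes (8.6 to 8.8, and 3.2) are outside the synopsis safety measures. Ectopic pregnancy has no named data item; 8.7 counts intrauterine sacs and heartbeats. Follow-up ends at the 8-12 week scan in Section 5 but extends to live birth in the synopsis, and Section 8 lists no items for later loss or neonatal outcome.

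**4. Illustration.** Arm sizes of 300 and 200 come from Section 7. The rates are assumptions: 40-60% of randomised women conceive, and 15-25% of those pregnancies are lost.

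- MIRI-TL: 300 × 0.40 × 0.15 = 18, to 300 × 0.60 × 0.25 = 45.
- Control: 200 × 0.40 × 0.15 = 12, to 200 × 0.60 × 0.25 = 30.

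That is 6% to 15% of randomised women in each arm. If pregnancy loss is on the consent list, none of these would be AEs.

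Now suppose the MIRI-TL doubles the rate of a harm. Power uses the two-sided 0.05 normal approximation, Φ{(|p1 − p2| − 1.96·SE0)/SE1}, where SE0 is pooled and SE1 unpooled. For 15% versus 30%, the pooled rate is (30 + 90)/500 = 0.24, SE0 = √(0.24 × 0.76 × (1/200 + 1/300)) = 0.0390, and SE1 = √(0.15 × 0.85/200 + 0.30 × 0.70/300) = 0.0366. Then (0.15 − 0.0764)/0.0366 = 2.01, giving power of 98%.

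| Assumed rates, control vs MIRI-TL | Share of events collected | Expected events, control / MIRI-TL | Power |
|---|---|---|---|
| 15% vs 30% | all | 30 / 90 | 98% |
| 15% vs 30% | half | 15 / 45 | 73% |
| 15% vs 30% | one tenth | 3 / 9 | 17% |
| 5% vs 10% | all | 10 / 30 | 52.5% |
| 5% vs 10% | half | 5 / 15 | 27% |
| 5% vs 10% | one tenth | 1 / 3 | 7.5% |

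The approximation is rough at the smallest counts. If an event type is wholly excluded, both arms show zero.

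**5. Reading a zero.** No AEs among 300 patients gives a one-sided 95% upper bound of 1 − 0.05^(1/300) = 0.99%. That bound applies only to event types that are collected.

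**The case against.** A reader might infer that the safety data would come back nearly empty whatever the device does. The documents do not support that. Device malfunctions are a named safety measure and are not subject to the 8.12 exclusion. Unanticipated device effects and any other event not on the consent list, apart from minor unrelated complaints, remain reportable, including events in users.

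A reader might also infer that embryo-mediated harm goes unrecorded or uncompared. That is not so either. Fertilisation counts and embryo morphology are collected, with Day 3 assessment explicitly in both groups. hCG, sacs, heartbeats, ongoing pregnancy and live birth are outcome data, and Section 7 gives chi-squared or Fisher's exact tests for categorical data in general. These data could show harm: on assumed rates, a fall in pregnancy rate from 50% to 35% with 200 and 300 patients would be detected with 92% power, and a fall to 40% with 60%.

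It is also fair to say that the IVF/ART relationship item does not strictly contradict the exclusion. An event absent from the consent list can still be judged related to IVF. And Section 3.1 only commits to collecting safety data; it defines no formal safety endpoint.

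All of this stands, and it limits the point. It does not remove it. Recording an outcome under secondary objectives does not make it part of the safety assessment, and a general test rule does not say which outcomes will be judged for safety.

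**Conclusion.** The concern holds in limited form. Section 8.12 removes an externally defined class of events before causality is judged, exempts neither serious nor possibly device-related ones, and gives the control arm no start point, contrary to the synopsis. Device incidents have no control counterpart. Pregnancy loss, ectopic pregnancy and birth outcome are not among the stated safety measures. AE counts plus device malfunctions therefore cannot, on their own, support the comparative safety purpose.

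The size cannot be fixed from the documents, because they contain neither the consent list nor any harm rates. The loss counts and the power table are illustrations on assumed rates. They bear on AE counts only if the event in question is on the list. The conclusion about comparability does not depend on them.

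**What to change.** 1. In 8.12, replace the reference to the clinic consent with a list, in the protocol, of stimulation and retrieval events that precede culture. Exempt serious or possibly device-related events from the exclusion.
2. Start AE collection at the beginning of embryo culture in both arms, with the same form and procedure, and reconcile 8.12 with the synopsis.
3. Prespecify as safety outcomes, whether or not they are known IVF risks: pregnancy loss, ectopic pregnancy, birth outcome as far as follow-up reaches, and embryo loss or damage during culture or handling. Record them identically in both arms.
4. Tabulate each by randomised arm with a confidence interval for the difference.

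The cost is protocol wording and a short extra CRF page. More events will be recorded, so the reported event rate will look less favourable.

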Study Start	April 2016

1. Introduction

The purpose of this clinical study protocol is to gather information regarding the performance and safety of a novel time lapse incubator compared to standard incubator systems. The MIRI-TL and the Culture Coin are CE Marked and have therefore fulfilled EU safety and performance criteria. In the US, 510(k) submission for both products is planned for Q2/Q3 2016.

As the sponsor of this clinical study, ESCO Medical has the overall responsibility for the conduct of the study, including assurance that the study will be performed according to the clinical investigation plan, applicable US Food and Drug Administration (FDA) and local regulation.

2. Background

The optimal goal of IVF should be the delivery of a healthy singleton baby and healthcare providers may be compelled via legal, financial, and moral obligations to reduce multiple pregnancies.¹⁻⁴ The clinical dilemma is how to restrict the number of embryos for transfer to prevent multiple births while at the same time maintaining or improving IVF success rates. The ability to selecting the highest quality embryo that is most likely to result in implantation becomes the key solution, however, this has proven to be challenging.

In the late 1990s, improved culture media enabled blastocyst culture, allowing embryos to develop in a petri dish for 2 to 3 additional days. Generally, about 40% of the embryos will form a blastocyst while others arrest in the culture dish during this extended period of incubation. It was broadly reported that blastocyst formation was a key embryo selection criterion for predicting successful implantation. Papanikolaou et al demonstrated in prospective randomized studies that embryo implantation rates and live birth rates were significantly improved with Day 5 transfer, as compared to Day 3 transfer.⁵⁻⁶ Because of improved implantation and live birth rates, blastocyst culture was widely adopted in clinics, in particular those which utilized single embryo transfer.

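### The 8.12 adverse event list has no causality item for the CultureCoin, although the primary objective covers the safety of both devices

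*Combined protocol and SAP*

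**What the plan says.** Section 3.1 has a single primary objective: "To collect safety and imaging data on the MIRI-TL and CultureCoin". The Introduction treats the two as separate products for regulatory purposes: "In the US, 510(k) submission for both products is planned for Q2/Q3 2016".

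Section 8.11 (Device Incidents) collects feedback on deficiencies, safety among them, affecting the "performance of the MIRI-TL and/or CultureCoin". Its data list has a field for the device or devices involved, and the sponsor must establish and document a root cause.

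Section 8.12 (Adverse Events) opens by naming both devices when it describes first contact. Its data list then holds these items that bear on attribution:

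- "Type of event and description";
- the investigator's "assessment as to the relationship of the AE to the MIRI-TL";
- the investigator's "assessment as to the relationship of the AE to IVF/ART procedures";
- the investigator's judgement on whether the event may be a UADE, with no device named.

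No item asks about the relationship to the CultureCoin. The synopsis says that adverse events and device malfunctions will be summarised, but not by device. Section 7 describes no safety analysis.

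**The concern.** The trial's primary purpose includes safety evidence on two products, both intended for US submission. For each adverse event, the investigator is asked to judge the relationship to one of them. The other is the dish that holds the eggs and embryos from Day 0, and no corresponding judgement is requested. At stake is whether the study report can state how many adverse events were considered related to the CultureCoin, and whether the MIRI-TL count is free of events that an investigator would have put down to the dish had the form offered that choice.

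**Working it through.** No arithmetic is needed to establish the point. The check sets the sections side by side and asks what each one records about each device.

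| Source | MIRI-TL | CultureCoin |
|---|---|---|
| 3.1, primary objective | named | named |
| 1, planned 510(k) | covered | covered |
| 8.11, incident record with device field and root cause | covered | covered |
| 8.12, device-specific causality item | yes | none |
| 8.12, UADE judgement | possible, device not named | possible, device not named |
| 8.12, type and description of event | yes | yes |

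**Step 1: count the causality items.** Of the two devices in the primary objective, one has an adverse event causality item and one does not.

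**Step 2: see whether another record supplies the missing answer.**

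- The UADE item can flag a dish effect. It does not say which device is meant, and by its name it covers only unanticipated effects.
- The description is kept for every collected event, but free text is not a causality judgement and cannot be tabulated as one.
- Section 8.11 identifies the device and the root cause. It does so for deficiencies, not for adverse events in subjects, and the protocol states no cross-reference between an incident record and an adverse event record. An event thought to be related to the dish, but without a recognised deficiency, has no place there.
- Section 8.12 sends the reader to a Section 10 on adverse event definitions and reporting. In the document, Section 10 is the reference list, so it offers no definition that extends the MIRI-TL item to the dish.

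**Step 3: see whether the analysis could recover the answer.** Under Section 8.1, MIRI-arm eggs go into a CultureCoin inside the MIRI-TL, and control eggs go into a standard dish inside a standard incubator. Dish and incubator change together between arms, so an arm comparison cannot separate their effects, however complete the adverse event data are. Case-by-case attribution is the only route, and for the CultureCoin the list does not ask for it.

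**Step 4: who is affected.** The plan is to recruit 300 MIRI-arm patients. Coding is affected only for those with a collected adverse event. Section 8.12 leaves out events well documented for IVF and minor health complaints, so this number may be small. The documents give no rate from which to estimate it.

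For illustration only: if the question were asked for all 300 and no event were attributed to the dish, the rule of three would give an upper 95% limit of about 3/300 = 1%. That shows the kind of statement a CultureCoin item would permit. It does not measure the defect.

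**The case against.** The strongest reply is that the dish is already covered. The CultureCoin is designed to sit in the incubator chamber and is used only in the MIRI arm. Section 8.11 begins with feedback on the MIRI-TL and then extends it to both devices. On that reading, MIRI-TL in the causality item stands for the whole system, and a dish-related event would be coded as device-related. The 8.12 list is also not stated to be exhaustive, and the form itself is not among the documents.

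Part of this stands. The system reading is plausible, and under it no device-related event would be missed. But 8.12 names the two devices separately a few lines before its causality item names only one, and investigators are not told to read the item more broadly. Even on the system reading, the answers could not be split by device, which two separate products need.

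It is also fair to say that an extra tick-box relies on investigator judgement, which may be difficult when the two devices are always used together. That limits how much the item can deliver. It does not favour asking the question for one device only.

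A reader might go further and infer that a CultureCoin-related event would be either charged to the incubator or lost, or that the CultureCoin count is zero by construction. The documents do not support this. Every collected event keeps its description whatever the causality answer, the relationship to IVF/ART procedures and potential UADE status are also judged, and a recognised dish deficiency is recorded against the dish under 8.11.

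**Conclusion.** The point holds as a minor gap in data collection. The MIRI-TL item is the only device-specific causality item, though not the only causality item. What is missing is a structured causality answer for the CultureCoin, so adverse events related to it cannot be tabulated from the causality data as the plan stands. The gap matters most for an event with no recognised dish deficiency, for which only the description and the UADE judgement could point to the dish.

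The conclusion assumes that the form follows the 8.12 list as written. If the form already has a CultureCoin item, only the protocol text needs correcting. The number of events affected is unknown. No sample size, power statement or planned test depends on this point.

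**What to change.** In Section 8.12, replace the single device item with two: relationship of the event to the MIRI-TL, and relationship of the event to the CultureCoin. Add a field that cross-references any Section 8.11 incident record for the same subject. In the safety summary, tabulate device-related events separately for each device, next to all adverse events regardless of attribution.

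The cost is one extra causality item and a cross-reference on the form, one table row, and slightly more work per event. Made before events are collected, the change is almost free. Made later, it requires each recorded event to be reviewed again.

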8.13 Study Exit

Study Exit data should be collected at the time a subject is exited from the study. A subject will be considered to have exited from the study for any of the following reasons including, but not limited to:

- Subject completed follow-ups required by the clinical protocol
- IVF cycle not completed or cancelled
- Subject requested to be withdrawn
- Subject terminated IVF treatment for personal reasons
- No availability of culture slots in the MIRI-TL
- Investigator requested that subject be withdrawn to protect the welfare of the subject
- Subject was lost to follow-up
- Subject was not compliant
- Other (specify)

A subject may elect to withdraw from the study at any time. The subject should notify the investigator if she wishes to withdraw from the study. The investigator and research staff should encourage all subjects to return for required follow-up visits. The investigator is free to withdraw a subject at any time if, in the investigator's opinion, it is in the best medical interest of the subject. A subject so withdrawn will be treated according to standard of medical care. The sponsor reserves the right to terminate this study at any time. Subject data will be included in the analyses up to the time that consent was withdrawn or up to the time that the study was terminated.

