4.1 CultureCoin

The 16-well CultureCoin (**Figure 2**) is a standard size (60mm) embryo culture dish with individual micro-wells aligned in a row in the center of the dish. Each micro-well is designed to accommodate a single patient's oocytes or developing embryos through the blastocyst stage and are culture individually. The 16-well CultureCoin is designed to fit in only one (1) position in one (1) of the individual six (6) incubator chambers, and each micro-well is identified to facilitate embryo tracking (for example, micro-well

Figure 2: CultureCoin

5. Number of Centers and Study Duration

The TiMMI study will include only one investigational site. This site will conduct the study under a single clinical investigation plan.

Expected study duration is 18 months including enrollment and follow-up. Subjects will be followed until pregnancy outcome has been determined (i.e. date of negative hCG test or 8-12 week clinical pregnancy ultrasound, if pregnant).

6. Study Design

This is a prospective, non-blinded, observational, randomized, double-arm study.

7. Statistical Methods and Analyses

Up to 500 subjects' embryos will be collected in this ongoing data collection protocol. We aim to recruit 200 patients in the standard culture group, and 300 patients in the MIRI-TL group.

Assuming that 25% of all inseminated oocytes would develop into blastocysts (based on published clinical data), at least 1300 inseminated oocytes (~163 patients) would be needed in each group to detect an increase in blastocyst proportion of 20% with 80% power and a significance level of 0.05 (two-tailed tests).

Assuming that time from insemination to start of blastulation (tSB) follows a normal distribution, and is 96h with a variance of 49h in euploid embryos, and 98h (variance 49h) in aneuploid embryos, ~405 blastocysts (1620 inseminated oocytes = 203 patients) in the MIRI-TL group will need to be biopsied to detect a significant difference in tSB (80% power, 0.95 confidence level, 2-tailed test). Since ~80% of all patients receive PGS at our clinical site, we will need ~255 patients in our MIRI-TL group.

To account for patient dropout and lower than expected oocyte retrieval per patient, we propose to recruit up to 500 subjects in this ongoing data collection protocol: 200 patients in the standard culture (SC) group and 300 patients in the MIRI-TL (MIRI) group.

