8.0 Patient Randomization

Patients will be randomized to the MIRI-TL group (MIRI) or the Standard culture group (SC) by randomization number generator through www.randomizer.org, using a number set from 1 to 500. Numbers 1-300 will be assigned to the study (MIRI-TL) group while numbers 301-500 will be assigned to the control (Standard Incubator).

8.1 Egg Retrieval and Fertilization-Day 0

Egg retrieval and fertilization follow the standard protocol in place at the clinical site. Insemination, by intracytoplasmic sperm injection (ICSI) will take place on Day 0 (egg retrieval day) following standard protocol currently in place at the clinical site. The fertilized eggs should be free of cumulus cells as much as possible. If the cumulus cells remain in place, they may interfere with the quality of the imaging. Immediately after micro insemination, eggs will be placed in individual wells within a CultureCoin (MIRI group), or a standard culture dish (SC group), and incubated in the MIRI-TL or standard incubator respectively. All eggs will be cultured in the standard fertilization media currently in place at the clinical site. At 20hr after insemination, the MIRI-TL imaging software will be Paused, and all embryos will be examined by the embryologist for successful fertilization (2PN). All normally fertilized eggs will be placed into a new CultureCoin (MIRI group) or standard culture dish (SC group) containing the standard embryo culture media, and incubated in the MIRI-TL or standard incubator respectively.

Once an embryo is assigned a micro-well location, it must remain in the same location throughout the study imaging period. Embryos assigned to the MIRI group will be imaged in the CultureCoin from Day 0 to Day 7. Images of the developing embryos will automatically be captured with the MIRI-TL Microscope. Data collected will include the following:

- Number of eggs inseminated

- Fertilization method
- Total number of fertilized eggs (2PN)

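### Lack of a MIRI-TL culture slot is a study-exit reason that only the MIRI-TL arm can meet, and the plan neither checks capacity before allocation nor keeps such patients in the analysis as randomised

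*Combined protocol and SAP*

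**What the plan says.** Section 8.13 opens its list with "A subject will be considered to have exited from the study for any of the following reasons including, but not limited to", and one entry is "No availability of culture slots in the MIRI-TL". It has no matching entry for the standard incubator.

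Section 8.0 sets the allocation: "Numbers 1-300 will be assigned to the study (MIRI-TL) group while numbers 301-500 will be assigned to the control (Standard Incubator"). It does not mention checking or reserving a chamber. Section 8.1 then separates the arms: "Immediately after micro insemination, eggs will be placed in individual wells within a CultureCoin (MIRI group), or a standard culture dish (SC group"). It adds: "Embryos assigned to the MIRI group will be imaged in the CultureCoin from Day 0 to Day 7".

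On capacity, section 4.1 says: "The 16-well CultureCoin is designed to fit in only one (1) position in one (1) of the individual six (6) incubator chambers". The inclusion criteria in the synopsis require patients to be "Willing to have all inseminated oocytes imaged by Miri".

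The only sentence on the data of patients who leave is in 8.13 (quoted here without its final word): "Subject data will be included in the analyses up to the time that consent was withdrawn or up to the time that the study was". It deals with withdrawn consent and early closure of the study, and a slot shortage is neither. Section 7 defines no analysis set by randomised arm. It allows for dropout without giving a rate or separating the arms.

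**The concern.** A patient allocated to standard culture cannot leave for want of a MIRI-TL slot, so this exit reason acts on one arm. If it operates after the random number is drawn, the MIRI-TL patients who remain are those for whom a chamber was free, while the standard-culture patients have passed no such filter.

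The filter need not be neutral. Whether a chamber is free depends on how busy the laboratory is. It may also depend on the patient: with 16 wells per CultureCoin and all inseminated oocytes to be imaged, more than 16 oocytes need a second CultureCoin and chamber. Oocyte number is plausibly related to blastocyst and pregnancy outcomes.

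The synopsis states the purpose as showing that MIRI-TL is non-inferior or superior to standard incubators in safety and efficacy. That claim rests on the randomised comparison. The comparison of time to start of blastulation (tSB) in euploid and aneuploid embryos lies within the MIRI-TL arm, so there the exits mainly cost sample size.

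**Working it through.** **1. The plan's own figures (section 7).**
- Blastocyst comparison, 25% against 30% (20% read as a relative increase), two-sided 0.05, 80% power: n = [1.96·√(2·0.275·0.725) + 0.8416·√(0.25·0.75 + 0.30·0.70)]² / 0.05² = 1251 oocytes per group. With continuity correction it is 1291, which agrees with the stated 1300. At 163 patients, this is 1300/163 ≈ 8 oocytes each.
- tSB comparison, difference 2 h, variance 49: n = 2·(1.96 + 0.8416)²·49/2² ≈ 193 per group, 386 in total. Dividing by the Wilcoxon efficiency of 0.955 gives 404, against the stated 405. Then 405/0.25 = 1620 oocytes, 1620/8 ≈ 203 patients, and 203/0.8 ≈ 254, stated as about 255.
- Recruiting 300 against 255 needed leaves room for 1 − 255/300 = 15% loss in the MIRI-TL arm.

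**2. Timing and handling, by section.**
- 8.0 (randomisation) comes before 8.1 (culture in the allocated system straight after injection), and no capacity step stands between them.
- 8.13 treats lack of a slot as an exit. Sections 7 and 8 do not say that outcomes are still collected or that the patient is analysed in her allocated arm.

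**3. How often a slot might be missing.** The documents give six chambers per unit, one CultureCoin per chamber, imaging from Day 0 to Day 7, and 300 MIRI-TL patients. They do not give the number of units or the enrolment period. The 18-month duration includes follow-up, so 18 months is an upper limit for enrolment. About 15.5 months leaves time for follow-up to the 8-12 week scan, and about 9 months for follow-up to live birth.

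Assumptions: random arrivals, one chamber per patient, seven-day occupancy. The load is a = 300 × 7 / enrolment days. The share finding every chamber full is the Erlang loss probability, from B₀ = 1 and Bₖ = a·Bₖ₋₁ / (k + a·Bₖ₋₁), taken to k = 6 (one unit) or k = 12 (two units).

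| Enrolment | Load a | One unit | Two units |
|---|---|---|---|
| 18 months (548 days) | 3.83 | 10.5% | 0.05% |
| 15.5 months (472 days) | 4.45 | 15% | 0.15% |
| 12 months (365 days) | 5.75 | 25% | 0.9% |
| 9 months (274 days) | 7.66 | 37% | 4.2% |

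Of 300 patients, 10.5% is about 32 and 37% about 111. If chambers were held for five days, one unit would give about 4% (18 months) to 23% (9 months).

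**4. Cost to the tSB comparison.** Biopsied blastocysts = 300 × (1 − loss) × 0.8 × 8 × 0.25. With an equal euploid/aneuploid split (assumed) and a t-test, power is 0.88 with no loss (480 blastocysts), 0.84 at 10% (432), 0.82 at 15% (408), 0.80 at 20% (384) and 0.77 at 25% (360).

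**The case against.** The strongest reply is that nothing states when the random number is drawn or when slots are checked. The exit list also covers cancelled cycles, which can happen before Day 0, so the slot entry might apply to consented patients not yet randomised. This stands as a limit: exit after allocation is inferred from section order and from the fact that only an allocated MIRI-TL patient needs a slot. The plan permits it but does not state it. If the site already confirms slots before randomisation, writing that down costs nothing.

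The oocyte mechanism is also weaker than it first looks. The plan implies about 8 oocytes per patient, half a CultureCoin. At the 20-hour check only normally fertilised eggs move to a new CultureCoin, so many patients with more than 16 oocytes might need a second chamber for about one day. The link with oocyte number is possible, not established.

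A reader might infer several stronger claims that the documents do not support:
- *The control arm loses nobody.* This is true for this exit reason only; the other listed reasons can apply to both arms.
- *About a third of the planned effect is bias.* If 15% are lost and their blastocyst rate is 10 points from the average, the arm's rate shifts by 0.15 × 10/0.85 ≈ 1.8 points against a planned 5. The 10-point gap has no source, and in the model that yields 15%, loss is unrelated to oocyte number, so it implies no such gap.
- *The data of these patients are discarded.* The plan is silent on them.
- *The bias cannot be repaired.* Demographics, IVF history and number of eggs inseminated are collected, so partial adjustment and sensitivity analyses are possible, though they rest on assumptions.
- *Unblinded staff could steer exits.* Whether a chamber is occupied is largely observable, and nothing suggests manipulation.

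Finally, the stated primary objective is to collect MIRI-TL safety and imaging data, and the calculation that sets the arm's size is within-arm with 15% to spare. That limits the damage to that part of the study but does not protect the between-arm comparison.

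**Conclusion.** The point holds in this form: the plan allows one-sided exit after allocation for a reason tied to laboratory workload and possibly to oocyte number, and nothing in it keeps such patients in the randomised comparison. The flaw lies in the rule and does not depend on any particular exit rate.

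Its size and direction are unknown. On the assumptions in the working, about 10% to 37% of MIRI-TL patients would find no slot with one unit and about 0% to 4% with two, so the loss could be large or negligible. No bias in the blastocyst or pregnancy rates can be quantified from the documents. For tSB the consequence is mainly precision: power stays near 80% up to about 20% loss on the plan's inputs with an equal euploid/aneuploid split.

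**What to change.** - **Section 8.0.** Add that a patient, whichever arm she would receive, is randomised only after the laboratory has confirmed enough free MIRI-TL capacity for her expected oocytes.
- **Section 8.13.** Record lack of a slot after allocation as a protocol deviation (8.10 already provides the form), not as a study exit. Outcomes continue to be collected. How the laboratory handles her embryos is left to the site.
- **Section 7.** State that these patients are analysed in the arm to which they were randomised, and that their number is reported.

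Simply deleting the entry would not be enough. The list is open-ended and closes with a free-text category, so such exits could continue without the code that lets them be counted.

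The cost is a short amendment and a capacity check before each draw. Some patients will not be enrolled in full weeks, and rare crossovers will slightly dilute the contrast between the arms.
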